## I. Background and Rationale

Overactive bladder (OAB) is a common condition with a prevalence ranging from 5.9% to 16.9% in the United States and has been found to increase with age. OAB has a negative impact on health related quality of life (QoL), and OAB patients have more anxiety and depression than controls. Primary treatment for OAB include behavioral modifications, such as decreased caffeine intake and timed voiding, and pelvic floor physical therapy. Second line therapy includes anticholinergic medicine/beta-3 adrenoceptor agonists. Unfortunately, compliance and adherence to these medications decreases over time likely due to side effects and/or efficacy.

Per AUA/SUFU guidelines, PTNS is a third line recommendation for OAB along with onabotulinumtoxinA (BTX) injection and sacral neuromodulation. The overall objective success (defined as  $\geq 50\%$  decrease in urge or urge urinary incontinence (UI) and 25% reduction in daytime and/or nighttime frequency) of PTNS has been published and ranges from 60% to 71%.

In the single sham-controlled trial (SUMiT: n=220), Peters et al reported that 54.5% of PTNS subjects had moderately or markedly improved bladder symptoms on global response assessments (GRA) compared to 20.9% of sham subjects ( $p < 0.001$ ). PTNS subjects also had statistically significant improvements in frequency, nighttime voids, voids with moderate to severe urgency and UI episodes compared to sham. Furthermore, significant improvements in bladder symptoms on GRA and quality of life (QoL) as measured with the Overactive Bladder Questionnaire (OABq) were observed after 12 but not 6 treatments, providing support for a 12-week treatment course. In another randomized, placebo controlled trial, Finazzi et al showed 71% response rate in the PTNS group compared to 0% in the sham, placebo group.

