## II. Objectives and Endpoints

- a. The primary endpoint will be assessed comparing GRA responses between sham and PTNS groups at one week ( $\pm$  3 days) post induction. This comparison will also be made for all other visits using t-tests or chi-square tests, as appropriate.
- b. Secondary endpoints will include comparisons between sham and PTNS groups looking at variables in the 3-day voiding diary and OABq-SF at one week ( $\pm$  3 days) post-induction. Voiding diary variables include frequency, nocturia, degree of urgency, and urge incontinent episodes. Changes from baseline will also be analyzed.

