Consented patients will complete the Overactive Bladder Questionnaire Short Form (OAB-q SF), 3-day voiding diary and enrollment questionnaire (demographics, medical history, concomitant medications, etc.) prior to study enrollment. A urinalysis via urine dipstick and pregnancy test (for women of child bearing potential) will be performed at screening. If the urinalysis is positive for leukocytes a urine culture will be sent. Patients with a positive urine culture may be treated per standard of care by the study physician. After treatment is completed, a repeat urine will be checked. If repeat urinalysis is negative, the subject will be allowed to complete the voiding diary and continue with study activities. The diary will be collected and reviewed at the first scheduled treatment visit (within 21 days from screening visit). If the patient meets the eligibility criteria, they will be randomized (1:1) into the sham or accelerated PTNS group.

Our goal is to have patients complete all three treatments within one week (7 days) but as there are always impedances (scheduling conflicts, illness, etc.) we will allow patients to complete all treatments within 2 weeks (14 days) if necessary. Patients will be allowed back-to-back treatments (i.e. two days in a row) if they should elect to do so. Adverse events and concomitant medications will be assessed at each treatment whether sham or active PTNS. GRA will be gathered at each visit beginning with the second induction treatment.

After completing the one-week induction consisting of three active or sham treatments, patients will receive a phone call three days ( $\pm$  1 day) after the last treatment to assess for any adverse events as well as remind them to start filling out their 3 day diary if they have not already begun to do so. This will also serve as a reminder phone call for their upcoming appointment.

One week post-induction ( $\pm$ 3 days), patients will return for an office visit. OAB-q SF, GRA and 3-day voiding diary will be collected. We will also assess for adverse events and concomitant medications at this visit. A blinding assessment questionnaire will be administered as well. A urinalysis will be completed.

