At 4, 8, and 12 weeks post-induction ( $\pm$  7 days), patients will return for follow-up appointments. Non-modified OAB-q SF, GRA and 3-day voiding diary will be collected and a urinalysis completed. Maintenance treatments (sham or active PTNS depending on treatment arm) will be given. Maintenance treatment will consist of a 30 minute treatment per standard of care. We will also assess for adverse events and concomitant medications at each of these visits.

After all study activities are complete, patients will be un-blinded at week 12 marking the end of the study. Those who were in the sham arm will be offered the opportunity to continue on to the open label phase of the study. Subjects in the open label phase will be offered the same accelerated treatments as those in the initial active PTNS treatment group. They will have up to 12 weeks to decide if they would like to continue on to the open label phase. This option will also be offered to those who had been previously randomized to the Sham group prior to the protocol amendment, even if they have completed their visit schedule. The follow up schedule will also be conducted in the same manner. Either of the groups can be offered re-induction per insurance requirements if they elect to do so with their

physician or can seek alternative treatments (BTX, sacral neuromodulation, etc.) per standard of care.

Our goal is to have patients complete all three open label treatments within one week (7 days) again, as there are always impedances (scheduling conflicts, illness, etc.) we will allow patients to complete all treatments within 2 weeks (14 days) if necessary. Patients will be allowed back-to-back treatments (i.e. two days in a row) if they should elect to do so. Adverse events and concomitant medications will be assessed at each treatment whether sham or active PTNS. GRA will be gathered at each visit beginning with the second induction treatment.

After completing the one-week open label induction consisting of three active treatments, patients will receive a phone call three days ( $\pm$  1 day) after the last treatment to assess for any adverse events as well as remind them to start filling out their 3 day diary if they have not already begun to do so. This will also serve as a reminder phone call for their upcoming appointment.

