## VI. Data Analysis

A biostatistician will perform all statistical analyses using SAS or similar statistical software. Descriptive statistics will be calculated. A completer analysis will be conducted for those who finish the study per protocol. The primary endpoint will be assessed comparing GRA responses between sham and PTNS groups at one week ( $\pm$  3 days) post induction. This comparison will also be made for all other visits using t-tests or chi-square tests, as appropriate.

Secondary endpoints will include comparisons between sham and PTNS groups looking at variables in the 3-day voiding diary and OABq-SF at one week ( $\pm$  3 days) post-induction.

Changes from baseline will also be analyzed. This comparison will also be made for all other visits using appropriate statistical tests.

Other statistical analyses will be completed as appropriate.

An intent to treat analysis which will identify any subject not assessed at 12 weeks post-induction as a failure will be conducted; a minimum of 1 induction treatment will be required to be included in the analysis.

Calculating Sample Size:

A sample size estimate of approximately 64 patients, 32 per study arm, was calculated using the Z test with pooled variance using a 58.3% responder rate in the PTNS group and a 21.9% responder rate in the sham group with a 5% significance level and 80% power; this also accounts for a 10% drop out rate. (Peters et al reported 58.3% and 21.9% responder rates for PTNS and sham groups respectively for an as-followed completer analysis and 54.5% and 20.9% responder rates for PTNS and sham groups respectively with an intent to treat analysis. We used the as-followed responder rates in calculating our sample size.)

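### The GRA is collected only at office visits, with no fallback for a missed visit, so some obtainable outcomes are dropped or coded as failures

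*Combined protocol and SAP*

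**What the plan says.** II. Objectives and Endpoints sets the outcome and its time: "The primary endpoint will be assessed comparing GRA responses between sham and PTNS groups at one week" (±3 days) after induction. I. Background and Rationale shows what a GRA response is, citing a sham-controlled trial in which "54.5% of PTNS subjects had moderately or markedly improved bladder symptoms on global response assessments (GRA").

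III. Methodology links the GRA to attendance throughout:
- In general: "GRA will be gathered at each visit beginning with the second induction treatment".
- One week after induction: "patients will return for an office visit. OAB-q SF, GRA and 3-day voiding diary will be collected".
- Weeks 4, 8 and 12 (±7 days): "patients will return for follow-up appointments. Non-modified OAB-q SF, GRA and 3-day voiding diary will be collected and a urinalysis completed".

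The only remote contact described comes after induction, when "patients will receive a phone call three days" (±1 day) after the last session. Its stated purposes are adverse events, a diary reminder and an appointment reminder. No reminder is described before week 12.

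VI. Data Analysis plans a completer analysis of patients who finish per protocol, and a second analysis: "An intent to treat analysis which will identify any subject not assessed at 12 weeks post-induction as a failure will be conducted", provided at least one induction treatment was given. It does not say which of the two is primary. On the sample size it says "this also accounts for a 10% drop out rate".

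**The concern.** A symptom rating can be given without coming to the clinic. Under this plan, a patient who will not or cannot attend gives no rating. Depending on the analysis, that patient is then removed or counted as a non-responder.

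Equal loss in both arms, coded as failure, shrinks the difference between arms. Loss that depends on benefit or discomfort can differ by arm and move the estimate in either direction. Dropping patients gives up randomized data, selectively if non-attendance is related to outcome.

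The failure rule adds a separate problem because it is keyed to week 12 while the primary endpoint is at week 1. Read literally, a patient with an observed week-1 response who misses week 12 becomes a failure in the intent-to-treat analysis, although no primary outcome was missing. A remote fallback at week 1 alone would not cure that.

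**Working it through.** **Inputs, all from VI. Data Analysis:** responder rates 58.3% (PTNS) and 21.9% (sham), 5% significance level, 80% power, Z test with pooled variance, 10% dropout, 32 per arm. The test is taken as two-sided; the plan does not say, but this reproduces its figure.

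**1. The plan's sample size.** The mean rate is (0.583 + 0.219)/2 = 0.401.

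n = [1.960·√(2·0.401·0.599) + 0.8416·√(0.583·0.417 + 0.219·0.781)]² / 0.364²

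= (1.3585 + 0.5416)² / 0.364² = 27.2, rounded up to 28 per arm. Then 28/0.9 = 31.1, rounded up to 32 per arm, or 64 in total. The stated figure reproduces.

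**2. Failure coding.** Assume a fraction m of each arm is missing and that missing patients would have responded like the others. Coding them as failures multiplies both rates by (1 − m). At m = 0.10:
- PTNS: 0.583 × 0.9 = 52.5%
- Sham: 0.219 × 0.9 = 19.7%
- Difference: 36.4 × 0.9 = 32.8 points instead of 36.4

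**3. Power at 32 per arm.** Exact power is the sum of binomial probabilities over all pairs of responder counts at which the uncorrected pooled Z test rejects. The normal approximation is shown beside it. Only the 10% is the plan's figure; the other losses are assumed.

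| Coded as failure, each arm | Rates | Exact power | Normal approximation |
|---|---|---|---|
| 10% (none retrieved) | 52.5% vs 19.7% | 80.5% | 79.3% |
| 5% (half of the 10% retrieved) | 55.4% vs 20.8% | 84.1% | 82.9% |
| 3% | 56.6% vs 21.2% | 85.4% | 84.3% |
| 0% (all retrieved) | 58.3% vs 21.9% | 87.4% | 86.2% |
| 20% | 46.6% vs 17.5% | 72.6% | 71.3% |

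The largest gain at the planned loss is 87.4 − 80.5 = 6.9 points. At 3% loss it is 87.4 − 85.4 = 2.0 points.

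**4. Completer analysis.** With 32 × 0.9 = 28.8 per arm and unchanged rates, approximate power is 82.2%, against 86.2% with nothing lost: about 4 points.

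**5. Unequal loss under failure coding (assumed splits).**
- 15% PTNS, 5% sham: 0.583 × 0.85 − 0.219 × 0.95 = 28.75 points; exact power 69.5%.
- 5% PTNS, 15% sham: 0.583 × 0.95 − 0.219 × 0.85 = 36.8 points, slightly above the true 36.4.
- No true effect (21.9% in both arms), 5% against 15% lost: 0.219 × (0.95 − 0.85) = 2.2 points of false difference.

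The direction of the error thus depends on which arm loses more patients.

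**The case against.** The plan has a good defence on power. It enlarged the sample for dropout, and even with 10% of each arm coded as failures, exact power is 80.5%. A reader might infer that the trial is underpowered, or that about 7 points of power are there to be recovered. The documents support neither. The 10% is a dropout figure for the whole study, and nothing says that 10% miss the week-1 visit. That visit follows three treatment sessions, has a ±3-day window and is preceded by a reminder call. The 87.4% also requires that every lost patient, including those who withdraw, can be reached.

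Nor does the plan neglect retention: it has the reminder call, visit windows and repeated GRA collection. Visits are still needed for urinalysis, for the week-1 blinding assessment and for maintenance treatment at weeks 4, 8 and 12. Office collection is a reasonable default, and the text does not support replacing visits with remote contact.

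Two objections limit the remedy. Waiting for a form by post and telephoning only afterwards would often overrun the ±3-day primary window. And a research nurse delivers the active and sham procedures, so that nurse knows the allocation; having that nurse read out a subjective primary outcome would add a bias route.

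Finally, the GRA form is not in the text reviewed. That the rating is self-reported and can be given by telephone is inferred from how the Background describes it.

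What stands is the absence of any fallback after a missed visit, and the failure rule keyed to week 12. Enlarging the sample replaces numbers but does not correct selective loss.

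**Conclusion.** The concern holds in a limited form. The GRA is tied to office attendance with no other route, so some obtainable outcomes will be dropped or turned into failures. The stated power is met even so. The gain in exact power from full retrieval is at most 6.9 points (80.5% to 87.4%), and about 2 points if 3% are missing. These figures assume the plan's responder rates, equal loss in both arms, and lost patients who respond like the rest.

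The stronger reason to act is that retrieval reduces loss that may differ by arm, which the sample-size allowance cannot repair. The documents give no attendance by arm, so the unequal-loss results illustrate the risk and do not predict it. Part of the failure coding comes from the week-12 rule itself, so the analysis text has to change along with data collection.

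**What to change.** **III. Methodology (one-week visit and follow-up visits), add:** A patient who misses the 1-, 4-, 8- or 12-week visit, including one who has stopped treatment, is contacted within the visit window and gives the GRA, and the OAB-q SF where possible, by telephone from a fixed script. The caller is an existing staff member who did not deliver that patient's treatment and does not know the allocation. A take-home form is an alternative. The date and mode of collection are recorded. A GRA given within the window counts as assessed; a later one is listed separately.

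**Also in III. Methodology:** add a reminder call before the week-12 visit.

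**VI. Data Analysis:** tie failure status for the primary comparison to the week-1 GRA, so that a patient with an observed week-1 GRA is not coded a failure for missing week 12. Add a sensitivity analysis that excludes remotely collected GRAs.

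**Cost:** protocol wording, printed forms and a few calls. All visits and the sample size of 64 stay as they are. The downside is that a few outcomes arrive by a different mode, which the sensitivity analysis can check.

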## III. Methodology

The aim of this study is to determine the efficacy of an accelerated course for percutaneous tibial nerve stimulation (PTNS) induction. The standard 12 weekly induction treatments may be a patient burden and a more rapid induction may speed up symptomatic improvement.

We anticipate enrolling 64 patients, in this randomized trial, 32 in each study arm. Patients will be recruited from Beaumont's Women's Urology Center, as well as private Urology offices. Eligible patients will be consented and randomized into 1 of 2 groups. Patients will be enrolled in the study and randomized:

- After all screening activities have occurred and it has been determined that the patient meets all inclusion criteria without the presence of exclusionary criteria.
- After the patient agrees to enroll and comply with the study protocol, regardless of study group assignment.

Patients will be randomized 1:1 to active PTNS treatment or Sham treatment

The process of randomization will be as follows:

- Randomization will be performed using a table of random numbers. Randomization envelopes will be provided by the study's biostatistician. Randomization assignment will be to either active PTNS treatment or Sham treatment. The randomization envelopes will be securely stored in a locked cabinet. The Research Coordinator(s) will ultimately be responsible for maintaining the confidentiality and security of the randomization envelopes.
- The biostatistician will prepare more envelopes, if necessary.
- After the participant is randomized, staff will complete the ***Subject Enrollment and Randomization Log***. The log may be stored in the locked cabinet with the envelopes. Ultimately the log will be stored in the regulatory binder.

All patients who enroll will be seen and treated at the Beaumont Urology clinical research suite.

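### No repeat pregnancy test or exclusion check is required before a sham patient's first active PTNS in the open-label phase, when the pregnancy test can be 30 weeks old

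*Combined protocol and SAP*

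**What the plan says.** All of the timing is in III. Methodology.

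- **Exclusion check.** Patients are randomized once "it has been determined that the patient meets all inclusion criteria without the presence of exclusionary criteria". The baseline diary, which supplies one of the inclusion criteria, is "reviewed at the first scheduled treatment visit (within 21 days from screening visit"), and randomization follows if the patient is eligible.
- **Pregnancy test.** The "pregnancy test (for women of child bearing potential) will be performed at screening". No other test is described.
- **Blinded phase.** At 4, 8 and 12 weeks, "Maintenance treatments (sham or active PTNS depending on treatment arm) will be given". A sham patient therefore stays on sham throughout. Under Sham Group, the sham needle does not pierce the skin and the tibial nerve is not stimulated.
- **Transition.** After all activities, "patients will be un-blinded at week 12 marking the end of the study". Sham patients may then enter open label and receive the active arm's accelerated course: "They will have up to 12 weeks to decide if they would like to continue on to the open label phase". Sham patients from before the amendment are also offered this, "even if they have completed their visit schedule".
- **Open label.** The text lists three active treatments, a phone call, GRA, OAB-q SF, diary, urinalysis at the later visits, maintenance treatments, and review of adverse events and concomitant medications. It lists no repeat pregnancy test and no repeat exclusion check.

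Section V excludes, among others, patients who are pregnant or planning pregnancy, have a pacemaker or implanted defibrillator, use neuromodulation or TENS, or have a current urinary tract infection.

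**The concern.** The sponsor judged that pregnant patients and those with certain devices should not enter the trial, and required a test to rule pregnancy out. For a sham patient, open label brings the first skin puncture and the first tibial nerve stimulation of the trial. That is when the screening safeguards matter most to this patient, and also when they are oldest.

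No study visit is scheduled during the decision period. Followed as written, the protocol would let a woman who became pregnant after screening receive active PTNS against its own exclusion, and no required step would detect the pregnancy.

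The wording adds some doubt about which restrictions apply in between. Week 12 is called the study's end, yet open label is also described as a phase of the study. The pregnancy exclusion and the requirement to keep InterStim off are both defined by the length of the study.

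**Working it through.** The documents state no figure for the age of these checks, so there is none to reproduce. The ages follow from the visit windows in III. Methodology.

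**Inputs (maximum of each window)**
- Screening to first treatment visit: 21 days.
- Blinded induction: 14 days (the goal is 7).
- End of induction to the week-12 visit: 12 × 7 + 7 = 91 days.
- Decision period: 12 × 7 = 84 days, assumed to start at the week-12 visit.

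**Step 1. Pregnancy test, performed at screening**
- Prompt entry after week 12: 21 + 14 + 91 = 126 days (18 weeks).
- Entry at the decision deadline: 126 + 84 = 210 days (30 weeks).

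**Step 2. Exclusion check, performed before randomization**

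The text does not fix the day. If the check is completed at the first treatment visit, when the diary is reviewed, the 21 days drop out:
- Prompt entry: 14 + 91 = 105 days (15 weeks).
- Decision deadline: 105 + 84 = 189 days (27 weeks).

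If it is completed at screening, the figures are those of step 1. At the deadline the range is therefore 189 to 210 days.

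**Step 3. Comparison with the active arm**

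An active-arm patient having the week-12 maintenance treatment has a pregnancy test up to 21 + 14 + 91 = 126 days old. The exclusion check is 105 to 126 days old. These equal the figures for a prompt open-label entrant. The excess for a late decider is 210 − 126 = 84 days, which is the decision period itself.

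**Step 4. Sensitivity to the windows**

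With a 7-day induction and on-time visits, the pregnancy test at the deadline is 7 + 84 + 84 = 175 days (25 weeks) old with no screening gap. With the full 21-day gap it is 196 days (28 weeks) old. The result does not depend on stretching every window.

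**Step 5. What the figures leave open**

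The 12 weeks limit the decision, not the start of treatment, so 210 days can be exceeded. For pre-amendment sham patients who have finished their visits, the text gives no date from which the 12 weeks run, so no upper bound can be computed.

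**Step 6. Who is affected**

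At most the 32 sham patients of the planned 64 can take this route. The pregnancy point applies only to women of childbearing potential among them. The documents give no expected uptake.

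**The case against.** **Safeguards remain.** Adverse events and concomitant medications are reviewed at each open-label treatment, and a urinalysis is done at the week-12 visit. Botox would probably appear as a medication, and a new pacemaker would probably surface in the review. The principal investigator is also responsible for patient safety. This stands, and it narrows the concern mainly to pregnancy, for which none of these is a test.

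**The absence cannot be fully verified.** The Schedule of Research Activities is damaged in the available copy. Its eligibility and pregnancy-test rows show a single mark each, at screening, which agrees with the prose but is not proof. Consent pages were not available. The point therefore rests on the protocol prose alone.

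**The study restrictions have an ordinary reading.** Open label is called a phase of the study, so the pregnancy and InterStim restrictions can reasonably be read as extending into it. That is fair, but one sentence would settle it, and a restriction does not replace a test.

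A reader might also infer stronger points that the documents do not support:
- *Interim Botox, sacral neuromodulation or re-induction feeds excluded patients into open label.* The sentence on these options reads most naturally as alternative care. A standard course ("The standard 12 weekly induction treatments may be a patient burden") spans 11 × 7 = 77 days and would fit within the 84, but that sequence is constructed rather than planned. The 6-month rule on earlier PTNS is tied to screening, not to open-label entry. Sacral neuromodulation is excluded only when active.
- *All checks are 30 weeks old.* Only the pregnancy test is fixed at screening; the exclusion check may be 27 weeks old.
- *The whole open-label course should be added to the age.* That course adds up to 14 + 91 = 105 days before the last treatment, but a check at entry would not shorten it, and the active arm has the same ageing within its course.

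**Conclusion.** The point holds as a gap in the protocol text, and the label is a cheap improvement. Neither the pregnancy test nor the exclusion check is required again before a sham patient's first active PTNS of the trial. At the decision deadline the pregnancy test can be up to 210 days (30 weeks) old and the exclusion check about 189 to 210 days (27 to 30 weeks). Pre-amendment sham patients have no stated bound. Prompt entrants are no worse off at entry than active-arm patients at week 12, so the gap concerns late deciders and pre-amendment patients, and chiefly pregnancy.

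This rests on the 12 weeks starting at the week-12 visit, on windows used in full, and on the prose rather than the damaged schedule. The documents do not size the risk. It would be wrong to infer any effect on the primary result: patients enter open label after un-blinding, so the randomized comparison and the sample size are unaffected.

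**What to change.** Before the first open-label treatment, at least for entrants who do not start promptly after the week-12 visit and for all pre-amendment sham patients:

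1. Repeat the urine pregnancy test in women of childbearing potential.
2. Re-confirm the safety-relevant exclusions on a short checklist: pacemaker or defibrillator, active neuromodulation or TENS, and current urinary tract infection.

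Also state that the pregnancy and InterStim restrictions apply through the open-label phase.

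The cost is a short amendment, one checklist per applicable entrant and one urine test where relevant. The downside is that a few sham patients may be found ineligible for open label. Nothing in the randomized phase changes.
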